### 9.6 Sub-Group Analyses

Analyses to examine the consistency of results across different subgroups will be performed for the primary safety and effectiveness endpoints for the following subgroups, and results will be reported using descriptive statistics:

- Age (>75 vs ≤75 years)
- Gender
- Diabetes (medically treated vs no diabetes or not medically treated)
- Renal insufficiency (eGFR: <30, 30-59, ≥60)
- Lesion length (<100 mm, 100-150mm, >150mm)
- Chronic Total Occlusion (CTO)
- Calcification (moderate vs severe)
- IVUS Sub-study at baseline, immediately post-IVL, and end of procedure
- Wounds at baseline
- Claudicant (RC 3) vs. CLI (RC 4 & 5)

	No.: CP 65007	REV. C
	TITLE: Disrupt PAD BTK II Study	
	CLASS: CLINICAL PROTOCOL	PAGE 42 OF 71

No formal hypothesis testing for subgroup analyses will be performed. However, to examine the consistency of results across different subgroups, the primary safety and effectiveness endpoints will be compared between subgroups using a logistic regression model including an intercept term and fixed effect for the subgroup, with corresponding 95% confidence interval and p-value presented.

	No.: CP 65007	REV. C
	TITLE: Disrupt PAD BTK II Study	
	CLASS: CLINICAL PROTOCOL	PAGE 43 OF 71

## 10.0 SAFETY EVENTS

---

Standard definitions and reporting requirements for reportable adverse events for the study are provided below. All adverse events will be coded using MedDRA.

*Note: For any of the Adverse Event Definitions listed below, diagnosis should be reported versus individual symptoms leading to diagnosis.*

### 10.1 Adverse Event Definitions

#### 10.1.1 Adverse Event (AE)

Untoward medical occurrence, unintended disease or injury, or untoward clinical signs (including abnormal laboratory findings) in subjects, users or other persons, whether or not related to the investigational medical device and whether anticipated or unanticipated.

*Note: Abnormal laboratory findings will be reviewed by the site Principal investigator (PI) and/or site Sub-investigator (Sub-I) who use their medical judgement to determine if these abnormal clinical signs are clinically significant (CS) or non-clinically significant (NCS). If the PI or Sub-I deem the abnormal laboratory finding to be clinically significant, it should be treated as an adverse event and documented as such. If found to be non-clinically significant, the PI/Sub-I should document this by writing "NCS" on source document and initial and date.*

*Note: This definition includes events related to the investigational medical device or the comparator.*

*Note: This definition includes events related to the procedures involved.*

*Note: For users or other persons, this definition is restricted to events related to the use of investigational medical devices or comparators.*

#### 10.1.2 Serious Adverse Event (SAE)

Adverse event that led to any of the following

- a) death,
- b) serious deterioration in the health of the subject, users, or other persons as defined by one or more of the following:
  - 1) a life-threatening illness or injury, or
  - 2) a permanent impairment of a body structure or a body function including chronic diseases, or
  - 3) in-patient or prolonged hospitalization, or
  - 4) medical or surgical intervention to prevent life-threatening illness or injury, or permanent impairment to a body structure or a body function,
- c) fetal distress, fetal death, a congenital abnormality, or birth defect including physical or mental impairment.

	No.: CP 65007	REV. C
	TITLE: Disrupt PAD BTK II Study	
	CLASS: CLINICAL PROTOCOL	PAGE 44 OF 71

*Note: Planned hospitalization for a pre-existing condition, or a procedure required by the CIP, without serious deterioration in health, is not considered a serious adverse event.*

#### **10.1.3 Adverse Device Effect (ADE)**

Adverse event related to the use of an investigational device.

*Note: This definition includes adverse events resulting from insufficient or inadequate instructions for use, deployment, implantation, installation, or operation, or any malfunction of the investigational medical device.*

*Note: This definition includes any event resulting from use error or from intentional misuse of the investigational medical device.*

*Note: This includes "comparator" if the comparator is a medical device.*

#### **10.1.4 Serious Adverse Device Effect (SADE)**

Adverse device effect that has resulted in any of the consequences characteristic of a serious adverse event.

#### **10.1.5 Unanticipated Serious Adverse Device Effect (USADE)**

Serious adverse device effect which by its nature, incidence, severity or outcome has not been identified in the current risk assessment.

*Note: Anticipated serious adverse device effect (ASADE) is an effect which by its nature, incidence, severity or outcome has been identified in the risk assessment.*

### **10.2 Adverse Event Device and Procedure Relatedness**

Based on clinical judgment, the Investigator must provide a determination of device and procedure relationship for adverse events according to the following categories:

- Causal Relationship (Definite) – The adverse event is clearly related to the study device: the event has a temporal relationship to the study device, follows a known pattern of response, or is otherwise logically related to the study device, and no alternative cause is present.
- Probable – The adverse event is likely related to the study device: the event has a temporal relationship to the study device, follows a known or suspected pattern of response, or is otherwise logically related to the study device, but an alternative cause may be present.
- Possible – The adverse event is unlikely related to the study device: the event does not follow a clear temporal relationship to the study device or does not follow a known pattern of response, or is otherwise possibly to be due to the subject's clinical state or other modes of therapy.

In some cases, the adverse event may not be adequately assessed because information is insufficient or contradictory and/or the data cannot be verified or supplemented. Maximum effort will be made to define and categorize the event and avoid these situations. If relatedness remains uncertain, then classify the event as "possible".

	No.: CP 65007	REV. C
	TITLE: Disrupt PAD BTK II Study	
	CLASS: CLINICAL PROTOCOL	PAGE 45 OF 71

- Not Related – The adverse event is clearly not related to the study device: the event has no temporal or other relationship to the administration of the investigational device, follows no known or suspected pattern of response, and an alternative cause is present.

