### 7.9.1 When and How to Withdraw Subjects

Subjects may be withdrawn at the medical discretion of the physician, or they may voluntarily withdraw their consent at any time without impact to their medical treatment.

	No.: CP 65007	REV. C
	TITLE: Disrupt PAD BTK II Study	
	CLASS: CLINICAL PROTOCOL	PAGE 37 OF 71

Prior to enrollment, the investigative site should provide contact information and detailed instructions to subjects on how to withdraw from the study. When a subject is withdrawn, all data obtained prior to the time of withdrawal may be submitted to the Study Sponsor and be included in the study database, unless otherwise requested by the subject in writing.

In the event a subject is lost to follow-up or cannot be contacted for post-treatment assessments, at least three attempts (two phone calls and a certified letter) will be made to locate the study subject, and these efforts will be documented. If the subject cannot be located, the subject's lost to follow-up status will be documented in the EDC and they will be exited from the clinical study.

Should the subject expire, an adverse event form and a study exit/withdrawal form must be completed. Physician assessment is required to determine if the cause of death was possibly, probably, or definitely related to the IVL System. If available, copies of the death certificate and/or an autopsy report should be included in the research records. The Investigator may need to provide written notification to the IRB/EC upon the death of the study subject, dependent on the IRB/EC policies.

	No.: CP 65007	REV. C
	TITLE: Disrupt PAD BTK II Study	
	CLASS: CLINICAL PROTOCOL	PAGE 38 OF 71

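### The relatedness category Possible is defined as unlikely related, so device-effect counts can include events the protocol itself calls unlikely, and investigators can code the same event differently

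*Combined protocol and SAP*

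**What the plan says.** Section 10.2 requires the investigator to rate each adverse event for its relationship to both the device and the procedure, using four categories: Definite, Probable, Possible and Not Related.

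- Probable opens with "The adverse event is likely related to the study device".
- Possible opens with "The adverse event is unlikely related to the study device". Its criteria begin "the event does not follow a clear temporal relationship to the study device or does not follow a known pattern of response", with a possible other cause as a further alternative.
- Not Related opens with "The adverse event is clearly not related to the study device".

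The section then deals with cases where "the adverse event may not be adequately assessed because information is insufficient or contradictory and/or the data cannot be verified or supplemented". Its instruction is "If relatedness remains uncertain, then classify the event as" possible.

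The category definitions name only the study device, although the procedure must also be rated.

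Section 10.1.3 defines an ADE as "Adverse event related to the use of an investigational device". Sections 10.1.4 and 10.1.5 build SADE and USADE on that definition. None of these sections says which relatedness categories qualify. The one explicit grouping is in Section 7.9.1, where the physician must decide whether a death was "possibly, probably, or definitely related to the IVL System".

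**The concern.** A label and its definition should lead two investigators to the same code. Here they point in different directions: the label says a device effect is possible, and the definition says it is unlikely. One code therefore receives three different judgements, namely a plausible device effect, an unlikely one, and an event that could not be assessed. They cannot be separated afterwards from the recorded code.

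What is at stake is the device-attributed part of the safety description. ADE, SADE and USADE status depends on an event being related to the device. Section 10.4.2 also sends device- or procedure-related events directly to the sponsor's Quality group. The study has no control arm (Section 6.0) and its objective is continued safety and effectiveness (Section 5.0), so attribution is an important way for a reader to separate device effects from background disease.

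**Working it through.** No arithmetic applies. The documents state no device-related rate, count or threshold, so there is no figure to reproduce. The check sets the provisions side by side.

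**1. The ladder of categories in Section 10.2**

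| Label | Opening judgement in the definition |
|---|---|
| Definite | clearly related |
| Probable | likely related |
| Possible | unlikely related |
| Not Related | clearly not related |

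The definitions step straight from likely to unlikely. No definition describes a relationship that is plausible without being likely.

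**2. Where three kinds of event go**

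- *A plausible but not likely device effect.* The opening words of Probable do not fit, and Not Related does not fit. The label Possible fits, but its definition does not. One investigator may follow the label and choose Possible. Another may follow the definition and move up to Probable.
- *An event judged unlikely but not excluded.* Not Related requires no temporal or other relationship, no known or suspected pattern, and an alternative cause, all together. If these are not all met, the definition sends the event to Possible. An investigator who reads only the labels may choose Not Related.
- *An event that cannot be assessed.* The default rule sends it to Possible.

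**3. Whether Possible counts as related**

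Only Not Related is called unrelated, and Section 7.9.1 places possible alongside probable and definite. The structure therefore favours counting Possible as related. This is an inference, because no section states the rule for ADE or SADE. On that reading, events that Section 10.2 calls unlikely enter the ADE and SADE counts and the Quality-group notifications.

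**4. What does not depend on this rating**

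- The primary safety endpoint (Section 5.1.1) combines all-cause death, above-ankle amputation and major reintervention. None of these requires a relatedness judgement.
- Major adverse events, clinically driven target lesion revascularization and major target limb amputation (Section 5.2) are CEC-adjudicated and are not defined by this scale.
- Section 9 plans no analysis of a device-related rate.
- In Table 3, SAE and SADE share one row with a 48-hour limit for reporting to the sponsor. USADE has the same 48-hour limit. Non-serious AE and ADE also share a row. Moving an event between related and unrelated does not change its deadline to the sponsor.

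**5. Procedure relatedness**

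The opening sentence of Section 10.2, and Sections 10.4.1 to 10.4.3, ask for the relationship to both device and procedure. The four definitions name only the device, so the procedure rating has no category wording of its own in the protocol.

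**The case against.** The strongest reply is that this is a wording slip with little consequence. No primary or secondary endpoint uses the rating, sponsor deadlines are the same either way, and sending uncertain events to Possible rather than Not Related is cautious. An inclusive category sends more events to the Quality group, not fewer. Section 12.0 makes the sponsor responsible for classifying adverse events, so the investigator's code is not the last step. Section 9.1 leaves clarifications of the analysis to the SAP, and Section 18.0 provides the case report forms separately. A rule for ADE tables, or procedure wording, may exist there.

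Most of this stands and limits the scope. The default is defensible, and the point is not an objection to it. But a later table rule cannot recover a distinction that was not recorded at the site, and sponsor review does not remove the conflict in the instruction given to investigators.

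A reader might also infer three stronger things that the documents do not support:

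- *That most events soon after the procedure must be coded Possible because Not Related is so strict.* Probable also admits an event with a temporal relationship, even where an alternative cause may be present.
- *That true device effects will be hidden because Possible will be treated as unrelated.* Nothing says so, and Section 7.9.1 points the other way.
- *That a planned safety rate becomes uninterpretable.* Section 9 plans no device-related rate. The accurate word for the descriptive counts is ambiguous.

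**Conclusion.** The point holds as a contradiction in an operative coding rule. Possible carries a definition that conflicts with its label, no definition covers a plausible but not likely device effect, and events that cannot be assessed share the same code. Descriptive ADE and SADE counts and Quality-group routing can include events the protocol calls unlikely, and coding can differ between investigators.

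The effect on counts rests on one assumption: that Possible is treated as related. The structure of Section 10.2 and the grouping in Section 7.9.1 support this, but no section states it for ADE or SADE. The number of events affected cannot be estimated from the documents.

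The correction is worth making because it is specific and cheap. It does not bear on the study's endpoints or on the time limits for reporting to the sponsor.

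**What to change.** In Section 10.2:

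- Replace the opening of Possible with wording that matches the label, for example: *may be related to the study device or procedure; a relationship cannot be ruled out, and an alternative cause is also plausible*. Bring the criteria that follow into line.
- Keep the default for events that cannot be assessed, and say explicitly that it is a conservative default.
- Word all four categories for the procedure as well as the device.
- State that definite, probable and possible count as related in ADE and SADE tables.

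Apply the change going forward by site memo. When tabulating events coded before the memo, note that the definition changed. Retrospective re-rating is not recommended: in an open single-arm study, events would be re-rated with outcomes already known. A separate flag for events that cannot be assessed is optional.

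The cost is a text amendment, a memo and a table footnote, plus a small coding discontinuity before and after the memo. With four categories, an event thought unlikely but not excludable will still be coded Possible. The new wording makes that explicit rather than contradicting the label.

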## 10.3 Device Deficiencies

### 10.3.1 Definitions

Device Deficiency is an inadequacy of a medical device with respect to its identity, quality, durability, reliability, usability, safety, or performance.

*Note: Device deficiencies include malfunctions, use errors, failure to fully cross lesion and inadequacy in the information supplied by the manufacturer including labelling.*

*Note: This definition includes device deficiencies related to the investigational medical device or the comparator.*

Device Malfunction is a failure of an investigational medical device to perform in accordance with its intended purpose when used in accordance with the instructions for use or Clinical Investigation Plan (CIP), or Investigator Brochure (IB).

*Note: An IB is deemed not required as the IFUs and product labelling together with available commercial product information is deemed sufficient information for the use of the device within its approved indication.*

### 10.3.2 Reporting

All device deficiencies and malfunctions will be documented on the eCRF and reported to the Study Sponsor within 48 hours after the designated study site personnel first learns of the event, and reported to the IRB/EC (if required) within the IRB/EC required timeframe. Device deficiencies and malfunctions will trigger an EDC notification to be sent directly to the Study Sponsor. All deficient/malfunctioned devices should be securely stored and prepared for return to Shockwave Medical.

In the event that EDC is unavailable, a paper Device Malfunction CRF must be submitted by the site to [[contact]](mailto:[contact]).

If a deficiency or malfunction meets the definition of a product complaint (any written, electronic, or oral communication that alleges deficiencies related to the identity, quality, durability, reliability, safety, or performance of a device after it is released for distribution), a Complaint Form will be completed by a Shockwave representative and entered into the company's complaint system, as per Shockwave Medical's internal procedure. The Shockwave Medical Quality representative is responsible for assessing the need for and submitting any Vigilance reports, and/or Medical Device Reporting (MDR) reports to the relevant regulatory agencies in line with country specific regulations and guidance documents, if required.

	No.: CP 65007	REV. C
	TITLE: Disrupt PAD BTK II Study	
	CLASS: CLINICAL PROTOCOL	PAGE 46 OF 71

## 10.4 Serious and Non-serious Adverse Event Reporting Requirements

### 10.4.1 AE Reporting Requirements

All AE information will be collected from enrollment through 24 months follow-up. Reporting will be carried out in accordance with national regulations. Site personnel will enter all AEs into an AE eCRF in EDC. AEs should be reported in the subject's medical records as applicable and on the Adverse Event Case Report Form (AE CRF). Data reported should include date of onset, treatment, resolution, and an assessment of both seriousness and relationship to the study device and procedure. AEs will be followed until the event has resolved (in the case of permanent impairment, the event will be followed until it stabilizes, and the overall clinical outcome has been ascertained).

Any AEs that meet IRB/EC reporting requirements must be reported per the institution's policy.

### 10.4.2 SAE Reporting Requirements

Any AE meeting any of the criteria for an SAE occurring at any time during the study (enrollment through 24 months) must be reported to the Study Sponsor within 48 hours after the designated study site personnel first learns of the event. The SAE must also be reported to the IRB/EC per the institution's policy for reporting SAEs. SAEs should be reported in the subject's medical records as applicable and on the Adverse Event Case Report Form (AE CRF). Data reported should include date of onset, treatment, resolution, and an assessment of both seriousness and relationship to the study device and procedure. SAEs will be followed until the event has resolved (in the case of permanent impairment, the event will be followed until it stabilizes, and the overall clinical outcome has been ascertained).

It is the responsibility of the Investigator to inform their IRB/EC of SAEs as required by their IRB/EC policies. The Investigator should forward a copy of this report to the Study Sponsor and file in the site regulatory binder.

SAEs will trigger an EDC notification to be sent directly to the Study Sponsor.

In the event that EDC is unavailable, a paper AE CRF must be submitted by the site to [[contact]](mailto:[contact]).

After data entry completion, a notification of SAE and/or device/procedure-related AE will be triggered and sent to the Study Sponsor, and any device and/or procedure related AE notifications will be sent directly to Shockwave Medical Quality for review.

### 10.4.3 Non-serious ADE Reporting Requirements

All ADE information will be collected from enrollment through 24 months. ADEs will be recorded in the subject's medical records as applicable and on the Adverse Event Case Report Form (AE CRF). Each ADE must be evaluated to determine if the event meets the definition of SADEs. Data reported should include date of onset, treatment, resolution, and an assessment of both seriousness and relationship to the study device and procedure. ADEs will be followed until the event has resolved (in the case of permanent impairment, the event will be followed until it stabilizes, and the overall

	No.: CP 65007	REV. C
	TITLE: Disrupt PAD BTK II Study	
	CLASS: CLINICAL PROTOCOL	PAGE 47 OF 71

clinical outcome has been ascertained). All ADEs must be reported to the Study Sponsor as soon as possible after the designated study site personnel first learns of the event.

#### **10.4.4 SADE Reporting Requirements**

All ADEs will be evaluated by the Study Sponsor or designee to determine if the ADE meets the definition of a SADE. All SADEs must be reported within 48 hours after the designated study site personnel first learns of the event. All SADEs should be reported to the IRB/EC in accordance with their requirements.

#### **10.4.5 USADE Reporting Requirements**

Investigators are required to submit a report of a USADE to the Study Sponsor as soon as possible, but not later than 48 hours after the designated study site personnel first learns of the event and to the ECs within the required timeframe. Investigators are required to report a UADE to the reviewing IRB/EC and the Study Sponsor as soon as possible, but in no event later than 10 working days after the Investigator first learns of the effect.

#### **10.4.6 AE and Device Deficiency Reporting Time Frames**

Table 3 summarizes the time sensitive reporting requirements for serious and non-serious adverse events and device deficiencies. The Study Sponsor or designee is the contact person for these reporting requirements.

